GENERAL AND SAFETY ASSESSMENTS																										
PK ASSESSMENTS																										
AMG 330 PK Collection ⁿ		X						X						X	X	X	X	X	X	X	X	X	X	X	X	
Pembrolizumab PK Collection (predose) (C1 only) ^o		X														X			X							
Pembrolizumab PK Collection (post dose) (C1 only) ^p		X														X			X							

	SCR (C1 only)	Treatment Period																	1 week infusion free interval ^a						Pembrolizumab monotherapy Cycles 2-3 ^b	EOT	SFU ^c	
		1 2 3 4 8 15 22 29 36 43 50																	57 58 59-63									
Cycle Day:		Pre-dose	0.5	1	2	3	4	6	8	12	16	20						EOI	0.5	2	4	8						
DISEASE ASSESSMENTS																												
Bone marrow aspirate/biopsy	X																X					X				X ^q		X ^r

CD = cluster of differentiation; ECG = electrocardiogram; ECOG = Eastern Cooperative Oncology Group; EOI = end of infusion; EOT = end of treatment;

PK = pharmacokinetic; SCR = screening; SFU = safety follow-up

^a If the investigator determines that the subject has derived treatment benefit, they may proceed to cycle 2 (Table 1-5). If the subject does not proceed to receive additional treatment cycles, they will proceed to end of study assessment on day 107 (30 days after last dose of investigational product).

^b If AMG 330 is discontinued, pembrolizumab may be continued as a monotherapy until disease progression, administered every 21 days, for a maximum of 35 cycles (approximately 2 years).

◦ Two safety follow-up visits should be performed: 30 days (+ 7 days) after the last dose of AMG 330 and 30 days (+ 7 days) after the last dose of pembrolizumab. If the 2 safety follow-up periods overlap, the 2 safety follow-up visits can be combined into one.

^d Hospitalization will be required at the start of study day 1 and for a minimum of 72 hours following initiation of AMG 330, after each AMG 330 dose level increase.

^e Adverse events will be collected from start of AMG 330 infusion on study day 1.

^f Clinical evaluations will include physical exam, ECOG, and weight. Screening only: demographics, medical history, and height will also be obtained.

⁹ Vital signs will be obtained at hour 1, 2, 3, 4, 6, 8, 12, 16, and 20 after start of AMG 330 infusion on study day 1 and after AMG 330 dose level increases. Vital signs will also be assessed prior to subject's discharge from hospital in order to detect possible signs and symptoms of infusion reactions.

^h Measurements to be taken in triplicate.

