
This study is will assess the safety and tolerability of the combination of AMG 330 with pembrolizumab and whether the inhibition of the PD-1/PD-L1 pathway by pembrolizumab will enhance the anti-AML activity of AMG 330. In cohort 1, subjects will be treated first with AMG 330 and then pembrolizumab will be subsequently administered to block PD-1 that became up-regulated in response to AMG 330. In cohort 2, pembrolizumab will be administered immediately prior to AMG 330 administration to block PD-1 that is expressed at baseline and any PD-1 up-regulated in response to AMG 330.

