4.1.2 Cohort 2 Design

Subjects in cohort 2 will receive both AMG 330 and pembrolizumab on day 1. All cycles are 57 days in duration. Pembrolizumab will be administered at a dose of 200 mg (Q3W) by a 30-minute IV infusion. The subject will then receive dexamethasone 8 mg. Dexamethasone will be given 1 hour prior to each step dose of AMG 330. If the subject does not develop a \geq grade 2 infusion reaction, or if the infusion reaction is reversible after the 1-hour observation period, the subject will start AMG 330 at a starting dose of [REDACTED] μ g/day for 3 days, followed by [REDACTED] μ g/day for 4 days, followed by [REDACTED] μ g/day for 7 days, and continue dosing as per [Table 4-3](#), increasing dose levels every 7 days up to [REDACTED] μ g/day as tolerated by subjects. Pembrolizumab will be administered at 200 mg IV once every 3 weeks. Subjects will continue [REDACTED] μ g/day of AMG 330 and pembrolizumab for 14 days. Cycle 1 will be followed by a 1-week interval without AMG 330 administration, and administration of pembrolizumab will continue non-interrupted on Q3W schedule. The AMG 330-infusion free interval may be extended up to 4 weeks (depending on safety, treatment response, and in case of prolonged marrow aplasia and cytopenia in aleukemic subjects) after consultation with the sponsor. Cycle 2 and all subsequent cycles will start with the initiation of AMG 330 administration and include the same step dose levels and duration as in cycle 1. The duration of AMG 330 step dose levels in cycle 2 and beyond can be shortened to 2 to 5 days if a subject tolerated the

investigational product in cycle 1 and based on the discussion and agreement between the investigator and the sponsor.

Table 4-3. Dosing for Cohort 2 (All Cycles)

AMG 330 Dose Level (μ g/day, cIV)	AMG 330 Days Administered	Pembrolizumab Days Administered (IV infusion)
	D1-3	D1
	D4-7	
	D8-14	
	D15-21	
	D22-28	D22
	D29-35	
	D36-42	
	D43-56	D43
(infusion-free period)	D57-64	

cIV = continuous intravenous; D = day; IV = intravenous

The overall study design is described by a study schema in [Section 1.2](#). The endpoints are defined in [Section 3](#).

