6.1.1.4 Pembrolizumab Dosage, Administration, and Schedule

Trial treatment should begin as close as possible to the date on which the subject is allocated/assigned. The pembrolizumab treatment to be used in this study is outlined below in [Table 6-2](#).

Schedule of pembrolizumab dosing and related assessments are specified in the Schedule of Activities ([Table 1-1](#), [Table 1-3](#), [Table 1-5](#)). Pembrolizumab will be administered as a dose of 200 mg using a 30-minute IV infusion. Sites should make every effort to target infusion timing to be as close to 30 minutes as possible. However, given the variability of infusion pumps from site to site, a window between - 5 minutes and + 10 minutes is permitted (ie, infusion time is 30 minutes - 5 minutes/+ 10 minutes). Following the completion of the pembrolizumab administration, the subject will be observed for 1 hour to monitor tolerability of the infusion.

For this study, an overdose of pembrolizumab will be defined as ≥ 1000 mg (≥ 5 times the indicated dose) of pembrolizumab. No specific information is available on the treatment of overdose of pembrolizumab. In the event of overdose of pembrolizumab, the subject should be observed closely for signs of toxicity. Appropriate supportive treatment should be provided if clinically indicated.

Table 6-2. Trial Treatment

Drug	Dose/ Potency	Dose Frequency	Maximum Length of Dosing	Route of Administration	Regimen ^a	Use
Pembrolizumab	200 mg	Every 21 days	Up to 35 cycles	Intravenous	Day 1 of each cycle. Starting at study day 15 (cohort 1), and study day 1 (cohort 2) (21-day cycles)	Experimental

^aPembrolizumab may be administered up to 3 days before or after each scheduled day 1 from pembrolizumab cycle 2 onwards.

When pembrolizumab administration falls on the same day as an AMG 330 dose level increase, pembrolizumab will be given first. After the pembrolizumab infusion is

complete, dexamethasone will be administered. The patient will then be observed for 1 hour. If the dose is well tolerated, the dose of AMG 330 may be increased to the next level. When pembrolizumab is administered as a monotherapy, dexamethasone will not be administered at the completion of the pembrolizumab infusion.

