6.1.4 Other Protocol-required Therapies

All other protocol-required therapies including dexamethasone and tocilizumab that are commercially available are not provided by Amgen. The investigator will be responsible for obtaining supplies of these protocol-required therapies.

Dexamethasone:

Premedication with dexamethasone is required prior to each AMG 330 treatment cycle and prior to each dose step for the prevention of CRS. Dexamethasone should be administered as a single IV dose (8 mg) within 1 hour of start of AMG 330 infusion or dose step, respectively. Dexamethasone will not be given as a premedication prior to pembrolizumab administration.

Approved

In the case of re-start of AMG 330 infusion after an infusion interruption of > 24 hours, dexamethasone (8 mg IV) should be administered within 1 hour prior to re-start and within 1 hour prior to the dose step.

For administration of dexamethasone after occurrence of CRS or other immune related adverse events, follow guidance in [Section 6.8](#) and [Table 6-3](#).

Tocilizumab:

For administration of tocilizumab after occurrence of CRS, follow guidance in [Section 6.8](#).

Throughout the study, Investigators may prescribe any concomitant medications or treatments deemed necessary to provide adequate supportive care except for those listed in [Section 6.1.7](#). Supportive care may include premedication with anti-emetics to limit treatment-related nausea and vomiting. Subjects should receive medications for treatment-induced diarrhea as clinically indicated. Anti-inflammatory or narcotic analgesics may be offered as needed. Packed red blood cell and platelet transfusions should be administered as clinically indicated.

Concomitant therapies are to be collected from the day of signing the informed consent, through the end of study. For all concomitant therapies collect therapy name, indication, dose, unit, frequency, route, start date, and stop date.

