
AE = adverse event; ALT = alanine aminotransferase; AST = aspartate aminotransferase; CTCAE = Common Terminology Criteria for Adverse Events; GI = gastrointestinal; irAE = immune-related adverse event; IV = intravenous; ULN = upper limit of normal
 
^a AST/ALT: > 3.0 - 5.0 x ULN if baseline normal; > 3.0 - 5.0 x baseline, if baseline abnormal; bilirubin: > 1.5 - 3.0 x ULN if baseline normal; > 1.5 - 3.0 x baseline if baseline abnormal
 
^b AST/ALT: > 5.0 to 20.0 x ULN, if baseline normal; > 5.0 - 20.0 x baseline, if baseline abnormal; bilirubin: > 3.0 - 10.0 x ULN if baseline normal; > 3.0 - 10.0 x baseline if baseline abnormal
 
^c AST/ALT: > 20.0 x ULN, if baseline normal; > 20.0 x baseline, if baseline abnormal; bilirubin: > 10.0 x ULN if baseline normal; > 10.0 x baseline if baseline abnormal
 
^d The decision to withhold or permanently discontinue pembrolizumab is at the discretion of the investigator or treating physician. If control achieved or ≤ grade 2, pembrolizumab may be resumed.
 
^e Events that require discontinuation include but are not limited to: Guillain-Barre Syndrome, encephalitis, Stevens-Johnson Syndrome and toxic epidermal necrolysis.
				

Pembrolizumab may cause severe or life-threatening infusion-reactions including severe hypersensitivity or anaphylaxis. Signs and symptoms usually develop during or shortly after drug infusion and generally resolve completely within 24 hours of completion of infusion ([Pembrolizumab Investigator's Brochure](#)). Dose modification and toxicity management guidelines on pembrolizumab associated infusion reaction are provided in [Table 6-4](#).

Table 6-4. Pembrolizumab Infusion Reaction Dose Modification and Treatment Guidelines

NCI CTCAE Grade	Treatment	Premedication at Subsequent Dosing
Grade 1 Mild reaction; infusion interruption not indicated; intervention not indicated	
 Increase monitoring of vital signs as medically indicated until the participant is deemed medically stable in the opinion of the investigator. 	None

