8.2.5 Adverse Events and Serious Adverse Events

8.2.5.1 Time Period and Frequency for Collecting and Reporting Safety Event Information

8.2.5.1.1 Adverse Events

The adverse event grading scale to be used for this study will be the CTCAE v5 and is described in [Section 11.4](#).

The investigator is responsible for ensuring that all adverse events observed by the investigator or reported by the subject that occur after first dose of investigational product(s)/study treatment/protocol-required therapies through the safety follow-up visit

or 30 days following cessation of study treatment, whichever is later, are reported using the Event CRF.

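### Cohort 2 adverse event collection starts at the AMG 330 infusion in the Schedule of Activities, although pembrolizumab is given first on day 1 and the protocol text and SAP count from that dose

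*Protocol*

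**What the plan says.** Table 1-5 in protocol Section 1.3 is the schedule for cohort 2. Its footnote e reads: "Adverse events will be collected from start of AMG 330 infusion on study day 1".

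The dosing order is given in three places:

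- Section 2.1: "In cohort 2, pembrolizumab will be administered immediately prior to AMG 330 administration".
- Section 4.1.2: if there is no infusion reaction of grade 2 or higher, or if the reaction is "reversible after the 1-hour observation period, the subject will start AMG 330".
- Section 6.1.1.4: the pembrolizumab "infusion time is 30 minutes - 5 minutes/+ 10 minutes", after which "the subject will be observed for 1 hour to monitor tolerability of the infusion".

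Two other places set the start of adverse event reporting. Section 8.2.5.1.1 makes the investigator responsible for all adverse events "that occur after first dose of investigational product(s)/study treatment/protocol-required therapies". SAP Section 5.4 defines a treatment-emergent event as one starting at or after the first dose of any investigational product, and SAP Section 5.1 names pembrolizumab as one of the two products.

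**The concern.** Cohort 2 has two different start times for adverse event collection, and the one in the visit schedule is the later. The time between them is not neutral. Section 6.2.2.2.2 says of pembrolizumab infusion reactions: "Signs and symptoms usually develop during or shortly after drug infusion". That is the interval the footnote leaves out.

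Treatment-emergent and treatment-related adverse events are primary endpoints (protocol Section 3), and Section 8.2.5.1.5 says they are reported on the Event CRF. If a site takes its start time from the schedule, a non-serious reaction to the first pembrolizumab dose may never be entered. The SAP would count that event, but it can only count events that are in the database.

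**Working it through.** The plan states no figure for this interval, so the check is a comparison of start points followed by simple arithmetic.

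**Start points in cohort 2, day 1**

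| Source | Collection or counting starts at | First drug covered in cohort 2 |
|---|---|---|
| Protocol Table 1-5, footnote e | start of the AMG 330 infusion | AMG 330 |
| Protocol 8.2.5.1.1 | after the first investigational product, study treatment or protocol-required therapy | pembrolizumab |
| SAP 5.4 with 5.1 | first dose of either product | pembrolizumab |

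The second and third rows are worded differently but have the same effect here: in cohort 2, pembrolizumab comes before the dexamethasone premedication as well as before AMG 330 (Section 4.1.2). The first row differs from both. Table 1-1 carries the same sentence for cohort 1, but there AMG 330 is the first investigational product, with pembrolizumab following on day 15, so cohort 1 is not part of this point.

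**Length of the interval**

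Inputs, all from Section 6.1.1.4: infusion of 30 minutes, allowed range 30 − 5 = 25 to 30 + 10 = 40 minutes; observation of 60 minutes.

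Interval = infusion time + observation time.

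- Nominal: 30 + 60 = 90 minutes
- Shortest: 25 + 60 = 85 minutes
- Longest, uninterrupted: 40 + 60 = 100 minutes

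This assumes AMG 330 starts as soon as the observation hour ends. An interrupted infusion or any delay only lengthens it.

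**How often it occurs**

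The footnote refers to study day 1, which occurs once per subject (Appendix 1), so there is one such interval per cohort 2 subject. No cohort 2 enrolment figure is stated. Section 9.2 gives only a minimum of 6 DLT evaluable subjects. For 6 subjects the nominal total is 6 × 90 = 540 subject-minutes (6 × 85 = 510 to 6 × 100 = 600). This describes person-time at the minimum evaluable count and says nothing about the number of events.

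**Subjects who never start AMG 330**

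Read literally, the footnote never opens collection for a subject whose reaction prevents AMG 330 from starting. That subject is still in the Safety Analysis Set, because SAP Section 6.1 admits anyone enrolled who received at least one dose of either drug.

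**After correction**

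With collection starting at the first dose of either product, the interval is 0 minutes.

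**The case against.** The strongest reply is that the plan already has the right rule in the right place. Section 8.2.5.1.1 is the dedicated adverse event section, and its obligation covers the interval in full. The SAP's derivation uses an Events CRF flag for whether an event began before the first dose of any product, so the form itself is not tied to AMG 330. Serious events are collected from consent (Section 8.2.5.1.2).

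Grade 3 or 4 pembrolizumab reactions also have a separate route. The DLT window opens on day 1, and the exception for grade 3 infusion reactions in Section 6.2.1 does not apply when the reaction is attributed to pembrolizumab. Staff must in any case assess reactions in this interval before AMG 330 can start, and other records may leave partial traces. Section 6.1.4 says: "Concomitant therapies are to be collected from the day of signing the informed consent, through the end of study". Infusion start and stop times also go on the CRF (Table 6-1).

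Most of this stands, and it narrows the consequence. For infusion reactions, the exposure is mainly to non-serious grade 1 and 2 events at a site that follows the footnote rather than Section 8.2.5.1.1. It does not remove the contradiction:

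- The documents contain no rule that the body text overrides the schedule, and the opening of Section 8 makes adherence to the Schedule of Activities mandatory.
- The CRF flag classifies events that have been entered and cannot recover one that has not.
- Observing a reaction at the bedside, or recording a drug given for it, is not the same as recording an adverse event.

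**Conclusion.** The concern holds. Table 1-5 footnote e is wrong as written for cohort 2 and conflicts with protocol Section 8.2.5.1.1 and SAP Section 5.4. The uncovered interval is nominally 90 minutes per subject (85 to 100 for an uninterrupted infusion), once per cohort 2 subject, assuming AMG 330 starts directly after the observation hour.

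The severity is minor. The textual conflict is certain; any data loss depends on a site following the footnote, and the documents give no rate at which that would happen or at which events would go unrecorded. No effect on reported incidence is claimed. The error is confined to the footnote: Section 8.2.5.1.1 and the SAP definition need no change.

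**What to change.** Reword Table 1-5 footnote e so that adverse events are collected from the first dose of any investigational product (AMG 330 or pembrolizumab) on study day 1. This matches SAP Section 5.4 directly, and in cohort 2 it has the same effect as Section 8.2.5.1.1.

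The cost is one footnote. Subjects are already under observation in that interval, so no visit, procedure or CRF page is added, and no dosing or clinical management rule changes.

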2.1 Study Rationale

Cluster of differentiation (CD)33 is a promising cell surface target for treatment of acute myeloid leukemia (AML), as it is expressed on the cell surface of more than 90% of leukemia isolates from patients with AML with a very high average antigen density (Krupka et al, 2014). CD33 was also found cell surface of virtually all AML patient samples (Krupka et al, 2014) and CD33 expression is restricted to the hematopoietic system (La Russa et al, 1992; Andrews et al, 1989; Andrews et al, 1986). AMG 330 is a bispecific T-cell engager (BiTE®) construct that binds both CD33 and CD3, and redirects T cells toward CD33⁺ cells. With the induced proximity, AMG 330 mediates T-cell cytotoxicity against AML blasts. Anti-AML activity of AMG 330 and other CD33/CD3 BiTE molecules has been previously reported (Westervelt et al, 2018; Ravandi et al, 2018). Recent assessment of preliminary efficacy demonstrated that 5 (10%) out 50 treated patients experienced complete remission (CR)/CR with incomplete recovery (CRI), while approximately 50% of treated patients experienced only a transient decrease in the number of AML blasts in bone marrow. This finding is in line with the current view that in AML, tumor-reactive T cell responses can be strongly impeded by various immune resistance including up-regulation of inhibitory checkpoints such as programmed cell death 1 (PD-1) receptor (Alfayez and Borthakur, 2018; Hobo et al, 2018). Indeed, pre-clinical findings demonstrate that the response to AMG 330 monotherapy may be suboptimal due to engagement of resistance mechanisms including up-regulation of PD-1 on T cells (Krupka et al, 2016). Current experience with AMG 330 shows upregulation of PD-1 expression in treated subjects with relapsed or refractory (R/R) AML (Amgen, data on file) providing a rationale for combining AMG 330 with PD-1 blockers to overcome the resistance. PD-1 expression on CD4+ and CD8+ lymphocytes appears to be AMG 330 dose-dependent and trends higher in non-responders (Amgen, data on file). Pembrolizumab is a humanized immunoglobulin G4 (IgG4) monoclonal antibody with high specificity and potency of binding the PD-1 receptor, thus inhibiting its interaction with programmed cell death ligand 1 (PD-L1) and programmed cell death ligand 2 (PD-L2) and is indicated for the treatment of patients across a number of indications. However, PD-1 inhibition demonstrated limited single agent efficacy in patients with R/R AML suggesting a need for rationally designed combinations of PD-1 inhibitors with other immuno-oncology therapies aiming to improve T cell mediated cytotoxicity and surveillance (Boddu et al, 2017).

This study is will assess the safety and tolerability of the combination of AMG 330 with pembrolizumab and whether the inhibition of the PD-1/PD-L1 pathway by pembrolizumab will enhance the anti-AML activity of AMG 330. In cohort 1, subjects will be treated first with AMG 330 and then pembrolizumab will be subsequently administered to block PD-1 that became up-regulated in response to AMG 330. In cohort 2, pembrolizumab will be administered immediately prior to AMG 330 administration to block PD-1 that is expressed at baseline and any PD-1 up-regulated in response to AMG 330.

2.2 Background

2.2.1 Disease

AML is the most common form of acute leukemia in adults in the United States (US), with a rising incidence possibly due to an aging population, increased environmental exposure, and an increase in the population of cancer survivors previously exposed to chemotherapy and therapeutic radiation. In 2014, an estimated 18 860 new cases of AML were expected in the US with approximately 10 460 deaths from this disease ([American Cancer Society, 2014](#)).

Outcomes for most patients with AML remain poor ([Burnett et al, 2011](#)). In particular, relapsed disease is associated with unsatisfactory outcomes in the majority of patients ([Ravandi, 2013](#)). Although the majority of patients with AML initially achieve CR, over 60% will eventually relapse after a variable period of remission. Using the traditional cytotoxic chemotherapy regimens, the likelihood of achieving a second CR is low especially if the first CR was short in duration, particularly if less than 1 year ([Estey et al, 1996](#)).

Cluster of differentiation 33 (CD33) provides a useful target antigen for the treatment of patients with AML, as it is expressed on the cell surface of more than 90% of leukemia isolates from patients with AML with a very high average antigen density ([Krupka et al, 2014; Tanimoto et al, 1989; Scheinberg et al, 1989](#)). It is not expressed on tissues other than the hematopoietic system.

The PD-1 receptor-ligand interaction is a major pathway hijacked by tumors to suppress immune control. The normal function of PD-1, expressed on the cell surface of activated T-cells under healthy conditions, is to down-modulate unwanted or excessive immune responses, including autoimmune reactions. PD-1 (encoded by the gene *Pdcd1*) is an immunoglobulin (Ig) superfamily member related to cluster of differentiation 28 (CD28) and cytotoxic T-lymphocyte-associated protein 4 (CTLA-4) that has been shown to

negatively regulate antigen receptor signaling upon engagement of its ligands (PD-L1 and/or PD-L2) (Greenwald et al, 2005; Okazaki et al, 2001). Therapeutic studies in mouse models have shown that administration of antibodies blocking PD-1/PD-L1 interaction enhances infiltration of tumor-specific CD8+ T cells and ultimately leads to tumor rejection, either as a monotherapy or in combination with other treatment modalities (Spranger et al, 2014; Curran et al, 2010; Pilon-Thomas et al, 2010; Weber, 2010; Hirano et al, 2005; Blank et al, 2004; Strome et al, 2003). Anti-mouse PD-1 or anti-mouse PD-L1 antibodies have demonstrated antitumor responses in models of squamous cell carcinoma, pancreatic carcinoma, melanoma, AML and colorectal carcinoma (Curran et al, 2010; Pilon-Thomas et al, 2010; Zhang et al, 2009; Nomi et al, 2007; Strome et al, 2003). In such studies, tumor infiltration by CD8+ T cells and increased interferon (IFN)-gamma, granzyme B and perforin expression were observed, indicating that the mechanism underlying the antitumor activity of PD-1 checkpoint inhibition involved local infiltration and activation of effector T cell function *in vivo* (Curran et al, 2010). Experiments have confirmed the *in vivo* efficacy of anti-mouse PD-1 antibody as a monotherapy, as well as in combination with chemotherapy, in syngeneic mouse tumor models (see the Investigator's Brochure).

2.2.2 Amgen Investigational Product Background: AMG 330

BiTEs® have been designed to direct T effector memory cells towards target cells. The proximity induced by the BiTE® triggers target cell specific cytotoxicity which closely resembles standard cytotoxic T lymphocyte activation.

AMG 330, targeting the surface antigen CD33, is a novel BiTE® which is being developed with the intent to treat patients with AML. Other CD33 expressing myeloid diseases, myelodysplastic syndrome and chronic myeloid leukemia, may be evaluated later in clinical development.

AMG 330 is currently being evaluated in the ongoing phase 1 dose escalation study in subjects with R/R AML (NCT02520427). One of the most frequent adverse events observed during the dose escalation study is cytokine release syndrome (CRS). An onset of grade 3 CRS during dose escalation led to an introduction of dose steps resulting in ameliorating frequency and severity of CRS. Subsequently, maximum tolerated dose (MTD) in the ongoing first-in-human phase 1a dose escalation study has not been reached. A detailed description of the chemistry, pharmacology, safety and efficacy of AMG 330 is provided in the [Investigator's Brochure](#).

2.2.2.1 Nonclinical Pharmacology: AMG 330

In vitro Pharmacology:

AMG 330 is a highly potent molecule selectively mediating redirected lysis of CD33⁺ cells, while viability of target-negative cells remains unaltered. The cytotoxic effect of AMG 330 is time- and dose-dependent, with mean concentrations inducing half-maximal target cell lysis ranging from 24 to 200 pg/mL (0.4 to 3.7 pM) with human effector cells.

In the presence of target cells, AMG 330 induced a polyclonal activation of T cells, which resulted in an up-regulation of the T cell activation markers CD25 and CD69, induction of granzyme B and perforin synthesis, T cell proliferation and release of cytokines like interferon- γ , tumor necrosis factor (TNF), interleukin (IL)-2, IL-10 and IL-6.

In primary AML samples AMG 330 induced an expansion of residual autologous memory T cells and an efficient elimination of AML blasts even at low effector cell: target cell ratios.

CD33 can be shed from the cell surface and was found in bone marrow plasma of AML patients at concentrations ranging from 0.4 to 29.6 ng/mL. A recombinantly produced extracellular domain of CD33 at concentrations of up to 100 ng/mL barely affected AMG 330-mediated redirected lysis of target cells and concomitant upregulation of CD25.

In vivo Pharmacology

Antitumor activity of AMG 330 was evaluated in AML xenograft models.

Intravenous treatment of non-obese diabetic/severe combined immunodeficiency disease (NOD/SCID) mice bearing subcutaneous EOL-1 tumors with AMG 330 (1, 10, and 100 μ g/kg/day) resulted in a statistically significant and dose-dependent tumor growth delay.

In an orthotopic AML model NOD/SCID mice were intravenously injected with MOLM-13 tumor cells. Administration of AMG 330 (2, 20, and 200 μ g/kg/day) resulted in a significant prolonged survival even at a dose of 2 μ g/kg/day AMG 330. In animals which survived until study termination on day 111, no CD33-positive target cells were detectable in blood, spleen and bone marrow.

2.2.2.2 Nonclinical Pharmacokinetics: AMG 330

After single intravenous (IV) administration, AMG 330 clearance (CL) was higher in mouse (53.5 mL/hour/kg) than in monkey (32 mL/hour/kg). The mean terminal half-life

($T_{1/2,z}$) of AMG 330 after a single IV bolus in mouse and 7 or 28 days of subcutaneous dosing in monkey was similar between these 2 species (4 to 8 hours); after 28 days of continuous intravenous (cIV) dosing $t_{1/2,z}$ of AMG 330 was 1.6 to 2.7 hours. The bioavailability of AMG 330 after subcutaneous dosing was 22% and ~40% in mouse and monkey, respectively. Dose proportionality was observed for exposure in both species after a single IV bolus injection in mouse and 7 days of cIV dosing in monkey; loss of exposure was observed after 28 days of cIV dosing due to the formation of anti-drug antibodies.

2.2.2.3 Nonclinical Toxicology: AMG 330

The potential toxicity of AMG 330 was evaluated in a Good Laboratory Practice (GLP)-compliant 28-day cynomolgus monkey toxicology study. AMG 330 was administered daily by cIV at 0, 3, 10, or 30 μ g/kg or subcutaneously (SC) at 25 μ g/kg. Two 30 μ g/kg-cIV females were euthanized on days 10 and 11 due to infections along the catheter port tract and/or at the skin contact points of the infusion jacket. The infections were considered secondary to AMG 330-related decreases in mature myeloid cells in the bone marrow and in circulating leukocytes. Other AMG 330-related findings were consistent with its expected pharmacology and included decreased leukocytes, which correlated with decreased T-lymphocytes, along with expected increased activated T-lymphocytes, and increased cytokine levels in all dose groups. Some animals at 30 μ g/kg cIV and 25 μ g/kg SC had clinical signs associated with inflammation/infection at the dose administration site that resolved after topical antimicrobial application and were able to complete the intended 28-day dose administration. In animals that survived to scheduled termination, there were no AMG 330-related macroscopic, organ weight or light microscopic changes. The changes observed in this study were consistent with the expected pharmacology of AMG 330. The highest non-severely toxic dose (HNSTD) was considered to be 10 μ g/kg/day cIV and 25 μ g/kg/day SC.

No combination toxicology studies have been conducted with AMG 330 and pembrolizumab.

